density	cancer diagnoses (screening + interval) per 1000 examinations*	Sensitivity (Scr / (Scr+Int))***	interval cancers (=1-Sensitivity)
total	6.2**		
<25%	2.5	82%	18%
<25% 25-50%	2.5 5.6	74%	26%
50-75%	7.6	66%	34%
>75%	8.0	45%	55%
from Kerlikowsl ** from the N Netherlands 19 *** calculated interval	rence of breast cancers ke et al. (6) for women of lational Evaluation Tea 90-2007 report (1) from the article from Va roup with >75% dens	50-69 years of age m for Breast Canco n Gils et al. (32) fo	er Screening in the or a 2-year screening
cancers per 1	000 mammographic so ion is that the MRI is	reening examinatio	ns is 4.4 (0.55*8.0).

stromal tissue, which is why women with >75% density can reach the same sensitivity using an MRI as with mammography among women with <25% dense tissue (i.e. 82%, see table). By adding MRI, we also expect that the proportion of interval cancers decreases to 1.44 per 1000 screening examinationss (0.18*8.0).

In the pre-randomisation design, it is necessary to take into account the fact that there are women who do not wish to take part after randomisation. Because this non-participation only occurs after randomisation, the non-participants must be included in the analysis according to the intention-to-treat principle. This means the required sample size becomes larger (35). A study by Berg et al. (23) on the added value of MRI in the ACRIN 6666 trial showed that 57.9% of the women contacted participated in the MRI substudy. For a number of women, money or not having insurance was the decisive factor. Without these reasons, the participation level would have been 66%. We expect to reach a participation of 66% because the cost of MRI examination is covered in our study.

In the intervention group, the expected interval cancer rate is 1.44/1000 screening examinations among the 66% who participated in the MRI examination and 4.4/1000 among the 33% that did not participate in the MRI examination. As a result, the interval cancer rate in the intervention group is 2.49/1000 screening examinations.

With a 1:4 ratio randomisation, 7,237 women are needed in the intervention group (of which 4,776 (66%) actually do take part in the MRI examination) and 28,948 women in the control group to show the difference between 4.4/1000 and 2.49/1000 as statistically significant (1-sided alpha=0.05) with a power of 80% after 1 screening round and the subsequent interval. This was calculated using the sample size software PASS.

Feasibility

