screening trial results such as these, and to compare the cost-effectiveness of different screening measures (38;39). It is a validated model that has been applied numerous of times successfully in evaluating different screening strategies. It is also one of the most commonly used breast cancer models by the Cancer Intervention and Surveillance Modelling Network (CISNET) consortium sponsored by the National Cancer Institute (40). In MISCAN, the individual life courses are generated as a Markov process of stages and transitions. For this, the characteristics of the study population (demographic data, risk factors) are fed to the model. The results of the screening and the scenarios as applied in the proposed experimental population-based screening study are estimated for a cohort of 1 million women with very dense breasts. The effects on mortality and life vears gained with the different screening scenarios are estimated at a period of 10 years after the start of the screening. The most important parameters in the model are the average duration of the preclinical stages that can be detected with screening, sensitivity of the screening test and improvement in prognosis after detection through screening. Outcomes of the model are the number of screen-detected tumours and interval cancers (including stage distribution), age-specific breast cancer incidence, stratified by stage, and age-specific breast cancer mortality.

Analysis of cost-effectiveness

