There have been reports of Nephrogenic Systemic Fibrosis (NSF) among patients with severe kidney dysfunction (see FDA website: http://www.fda.gov/Drugs/DrugSafety/ucm223966.htm#aihp). NSF is not described with patients with normal kidney functions. Severe kidney dysfunction is therefore an exclusion criterion for this study.

2) With the MRI examination, there is a chance of a false positive result with uncertainty, followed by extensive further and possibly invasive examination. How often this will happen in this population is not known and is also subject of the trial. The best indication we have comes from a recently published abstract (23) on the MRI substudy of the ACRIN 6666 trial (10). This study shows that based on MRI, 17% of the participants underwent further examinations (imaging or biopsy) that were in retrospect unnecessary. Nine percent underwent, in retrospect, an unnecessary biopsy. Based on histopathological research, it turned out the abnormalities of these patients were benign.

Participants will be informed thoroughly on the increased probability of false positives. Unnecessary invasive examination will be avoided as much as possible by looking back at the original mammographic examination, by assessing the MRI BI-RADS 3 results centrally and by scheduling a follow-up MRI after 6 months for this category and finally, by carrying out a target ultrasound before a possible biopsy.

3) There is a chance at being diagnosed with a relative indolent tumour that would never have been noticed if an MRI screening had not taken place (overdiagnosis). Overdiagnosis is inherent to screening: in the Dutch population-based screening program it is estimated that about 8% of the breast tumours discovered by screening would never have been diagnosed clinically in the absence of a screening programme (47). There are no estimates known yet on overdiagnosis in high-risk groups screened by MRI. We do not expect the overdiagnosis percentage to be higher in our study compared to the current population-based screening program because the ductal carcinoma in situ (DCIS) that plays a central role in the overdiagnosis problem, is actually easier to detect with mammography than with MRI (25;26). Besides, Kuhl et al. (48) have shown that the sensitivity of MRI for DCIS is especially high for the high-grade lesions that are most likely clinically more relevant.

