Overdiagnosis cannot be assessed for an individual, but our research is set up to get a better understanding of the degree of overdiagnosis on a population level. If the total number of tumours discovered in the MRI group (screening tumours) is greater than in the control group but the number of

interval cancers does not decrease proportionally, this could be an indication of overdiagnosis.
12. Information, consent
The information and consent of the participants will be in accordance with the Central Committee on Research involving human subjects (in Dutch: Centrale Commissie Mensgebonden Onderzoek (CCMO)) regulations.
Potential participants for the experimental population-based screening study will be recruited via the Dutch population-based mammography screening program. After randomisation, the intervention group will receive an information package through the mail about the study, consisting of the following documents: a cover letter from the screening organisation, information for the participants with the consent form, flow chart, MRI examination questionnaire and the 'General medical scientific research with human subjects brochure'. In the cover letter, the women are asked – even if they are not interested in participating – to log in to the website www.juliuscentrum.nl/dense-studie . The login codes are provided in the information for the participants. If the woman is not interested in the study, the procedure is merely unregistering with an option to indicate the reason thereof. Women who do wish to participate in the study, register on the website and indicate they are interested in participating. Then the woman enters her personal data so she can be contacted by telephone by the research team. During this telephone conversation, the study is explained again and the woman has the opportunity to ask any remaining questions. If a woman decides to take part in the study, the study team employee will send the consent form to the MRI examination. If the woman indicates over the telephone to want more time to make a decision, a later time is agreed on to call again. An appointment is scheduled for the MRI examination for those women who do wish to participate in the study. The MRI appointment will be confirmed in writing.
The information flowchart is also annexed to the information for the participants.
13. Ethical assessment
Not submitted for approval by Medical Ethical Committee.
 14. Funding

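### The overdiagnosis rule in Part 7 has no interval: at the planned size chance alone meets it about half the time in round 1, and the trial can neither show nor exclude the 8% cited

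*Combined protocol and SAP*

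**What the plan says.** Point 3 of the risk list that precedes section 12 of Part 7 deals with overdiagnosis. It cites an estimate of about 8% of screen-detected tumours for the current Dutch programme and notes that no estimate exists for high-risk groups screened by MRI. It then gives an expectation: "We do not expect the overdiagnosis percentage to be higher in our study compared to the current population-based screening program". On what the trial can add, it says "our research is set up to get a better understanding of the degree of overdiagnosis on a population level". The rule begins "If the total number of tumours discovered in the MRI group (screening tumours) is greater than in the control group" and continues that, if interval cancers do not fall in proportion, this could point to overdiagnosis.

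Section 7 (sample size) covers interval cancers only: "With a 1:4 ratio randomisation, 7,237 women are needed in the intervention group", "of which 4,776 (66%) actually do take part in the MRI examination", with "28,948 women in the control group". The basis is one-sided alpha 0.05 and 80% power after one round and the following interval.

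Section 6 gives the separation of real benefit from mere overdiagnosis as one reason for parallel groups. Section 9 describes no overdiagnosis analysis. On the simulation model it says: "Outcomes of the model are the number of screen-detected tumours and interval cancers (including stage distribution), age-specific breast cancer incidence", followed by mortality. Overdiagnosis is not named there, and effects are taken at 10 years from the start of screening.

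**The concern.** The rule compares two noisy quantities and gives no estimator, horizon or interval. Three things follow.

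- Women enter only after a negative mammogram, so controls have no screen-detected tumours in round 1. A single MRI detection makes the first half of the rule true.
- The second half then depends on whether extra detections exceed interval cancers averted. With about 14 MRI-detected tumours in the intervention arm, that is close to a coin toss when nothing is overdiagnosed.
- A trial sized for a large fall in interval cancers is not thereby sized for a small excess in total incidence.

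At stake is how one of the listed harms is reported. A positive reading could be chance. A negative reading could be taken as reassurance that the data cannot give.

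**Working it through.** **Inputs** (Part 7, section 7): 7,237 and 28,948 women; 4,776 scanned; 8.0 cancers per 1000 per round, of which 4.4 interval and so 8.0 − 4.4 = 3.6 mammography-detected; interval rate with MRI 1.44. Section 6 gives three rounds in six years.

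**Plan's own figure.** Pooled two-proportion formula, 1:4, one-sided 0.05, 80% power. With 0.66 × 1.44 + 0.34 × 4.4 = 2.446 per 1000 against 4.4, n = 7,243, which matches 7,237. (The printed 2.49 gives 7,617; this does not affect the present point.) The size is reproduced, and it concerns interval cancers only.

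**Round 1 under the rule.** The plan states no MRI yield. The one implied by its interval rates is 4.4 − 1.44 = 2.96 per 1000 scans.
- MRI-detected tumours: 4,776 × 0.00296 = 14.1.
- Interval cancers, intervention arm: 7,237 × 0.0044 − 14.1 = 17.7.
- Interval cancers, controls: 28,948 × 0.0044 = 127.4, or 31.8 scaled to 7,237 women.
- Expected excess: 14.1 − (31.8 − 17.7) = 0, that is, no overdiagnosis and no lead time.

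I read *in proportion* as one interval cancer averted per extra detection. In a Poisson simulation with these means, extra detections exceed interval cancers averted in 48% of trials.

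**Precision.** Excess = intervention count − control count × 7,237/28,948. With equal true cumulative incidence p (lead time fully removed), SE = √[7,237 p (1 + 7,237/28,948)] and the half-width is 1.96 SE. For round 1, p = 0.0044: SE = √(31.84 × 1.25) = 6.31, half-width 12.4 tumours, and 12.4/14.1 = 87%.

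Over three rounds p is 3 × 4.4 + 2 × 3.6 = 20.4 per 1000, or 24 with a mammogram after the last interval. Other yields are assumptions: 2.96 + 0.67 × 3.6 = 5.37 per 1000 scans if MRI also brings forward 67% of next-round tumours, and 0.82 × 8.0 = 6.56 if it finds 82% of all cancers.

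| Horizon (p per 1000) | Yield per 1000 scans | Half-width, tumours | MRI-detected | Half-width as share |
|---|---|---|---|---|
| Round 1 and interval (4.4) | 2.96 | 12.4 | 14.1 | 87% |
| Plus next screen (8.0) | 2.96 | 16.7 | 14.1 | 118% |
| Plus next screen (8.0) | 5.37 | 16.7 | 25.7 | 65% |
| Plus next screen (8.0) | 6.56 | 16.7 | 31.3 | 53% |
| Three rounds (20.4) | 2.96 | 26.6 | 42.4 | 63% |
| Three rounds (24) | 2.96 | 28.9 | 42.4 | 68% |
| Three rounds (24) | 6.56 | 28.9 | 94.0 | 31% |

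**On the base of the 8%**, all screen-detected tumours in the intervention arm (7,237 × 0.0036 = 26.05 added per later mammogram):

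| Horizon | Screen-detected | Half-width as share | 8% in tumours | SE under no excess |
|---|---|---|---|---|
| Round 1 plus next screen | 14.1 + 26.1 = 40.2 | 41% | 3.2 | 8.5 |
| Three rounds (20.4) | 42.4 + 52.1 = 94.5 | 28% | 7.6 | 13.6 |
| Three rounds (24) | 42.4 + 78.2 = 120.6 | 24% | 9.6 | 14.7 |
| Three rounds (24), yield 6.56 | 94.0 + 78.2 = 172.2 | 17% | 13.8 | 14.7 |

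Two-sided 5% power for an 8% excess is between 5% and 15% over all rows of both tables. For 80% power over three rounds the excess must be about 2.80 SE: 90% to 97% of MRI-detected tumours at the 2.96 yield (2.80 × 13.6/42.4 and 2.80 × 14.7/42.4), and 44% at 6.56 (2.80 × 14.7/94.0).

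**The case against.** The plan does not promise to measure overdiagnosis. It speaks of better understanding and of a possible indication, in a risk section. Overdiagnosis is not among the four research questions. Section 6 supports a modest reading: parallel groups are needed to look at the question at all, which is a claim about design and not about power. With no earlier estimate for this group, a wide one still adds something. All of this stands, and it is why the point is small.

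Four stronger readings are tempting and are not supported.

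- *The half-widths of 63% to 87% can be set directly against the 8%.* They are shares of MRI-detected tumours, while the 8% is a share of all screen-detected tumours. They also rest on one yield that the plan does not state.
- *A null result would be compatible with most MRI-detected tumours being overdiagnosed.* That needs a half-width above 50%. It holds at the 2.96 yield and fails at 31%. Nor does the plan say that it will read a null as reassurance.
- *The rule compares raw counts across 1:4 arms.* The sentence is loose, but sections 6, 7 and 9 work in rates and proportions, and an analyst would do the same here.
- *The plan overlooks that MRI overdiagnosis adds to that of mammography.* Point 3 already defines it as a tumour that would have gone unnoticed without the MRI.

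The model's listed incidence outputs would also allow an excess to be derived. What is missing is the named output and a horizon beyond 10 years.

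**Conclusion.** The point holds as a cheap improvement. The rule has no interval, its first condition is met in round 1 by any MRI detection, and its second is met by chance about half the time at the plan's rates. The 95% half-width is about 31% to 118% of MRI-detected tumours, or 17% to 41% on the base of the 8%. In every case worked, an interval centred on 0% or on 8% covers both values. Very large overdiagnosis could still be signalled.

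This rests on the plan's incidence and uptake, on assumed MRI yields of 2.96 to 6.56 per 1000 scans, on independent Poisson counts, and on lead time being fully removed, which favours the plan. Using 90% intervals, to match the one-sided 0.05, narrows every figure by about 16% (1.645/1.96 = 0.84) and changes no conclusion. The primary analysis and the sample size are unaffected.

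**What to change.** 1. In point 3 of the risk list, replace the rule with the difference between arms in cumulative breast-cancer incidence per 1000 women randomised (screen-detected plus interval cancers, over all rounds), with its 95% CI.
2. In section 9, add overdiagnosis to the MISCAN outputs: tumours with MRI minus tumours without MRI, over a lifetime horizon.
3. State in point 3 that the trial estimate will be imprecise, and that absence of a signal will not be read as absence of overdiagnosis.

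The cost is a little extra modelling and a stated capability that looks less favourable. No additional participants, visits or data are needed.
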